6.2.6 Length of ICU stay

Length of ICU stay will be compared between groups using Wilcoxon Rank Sum tests. As in the above analyses, this will be truncated at 60 days.

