1. BACKGROUND AND SIGNIFICANCE

1.1 Scope of the Problem

The worldwide incidence of sepsis has been estimated at more than 23 million cases⁶ and sepsis contributes to more than a third of all hospital deaths in the United States.^{7,8} Mortality for those in septic shock with elevated lactate is more than 40%.⁹ In addition to high short-term mortality, sepsis is associated with significant post-discharge morbidity and mortality.¹⁰⁻¹⁵ The economic burden for participants suffering from sepsis is staggering with an estimated yearly financial burden of \$17 billion.¹⁶ Treatments are generally limited to antibiotics and intravenous fluids while providing support to maintain organ function.^{17,18}

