1.2 Existing Interventions

To date, numerous interventions have been tested for participants with sepsis and septic shock with limited, if any, success.¹⁹⁻²² Recently, three large studies found no benefit from early goal directed therapy over usual care in emergency department participants with sepsis.²³⁻²⁵ Other recent studies focusing on hemodynamics, fluid therapy, and transfusions have also failed to show a significant benefit in this participant population.²⁶⁻²⁸ Previous studies focusing on immunomodulatory therapies or drotrecogin alfa have likewise shown disappointing results.²⁹⁻³⁵

1.3 Renal failure is a common sequela of septic shock and is associated with poor outcomes. Renal failure has been estimated to occur in 23% of patients with severe sepsis and 51% of patients with septic shock.³⁶ Further, the development of renal failure during sepsis or septic shock portends a significantly worse outcome.³⁶ In one study of patients with septic shock, there was a step-wise increase in mortality with worsening AKI.³⁷ These data suggest that attenuating kidney injury in sepsis will improve outcomes.

1.4 Thiamine (vitamin B1) is an essential component of mitochondrial energy production and may reduce oxidative stress. Thiamine is a key component in aerobic metabolism, working as a cofactor for pyruvate dehydrogenase. When thiamine levels are insufficient, pyruvate is unable to enter the Krebs Cycle, and pyruvate is converted to lactate, rather than acetyl-coenzyme A.^{24,25} Relative thiamine deficiency, therefore, causes a shift in metabolism to the anaerobic pathway, resulting in elevated serum lactate levels. Thiamine is also a critical component of the pentose phosphate pathway, which may reduce oxidative stress.^{9,10} As the kidney maintains a high mitochondrial abundance relative to other organs,⁸ it may be especially susceptible to perturbations in mitochondrial function.

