1.5 Thiamine may attenuate renal injury in patients with septic shock. In a *post-hoc* analysis of data collected during a randomized trial of thiamine vs. placebo,³ patients who received thiamine were less likely to require renal replacement therapy (RRT) and had lower creatinine levels over time as compared to patients who received placebo.⁴ That study, however, was limited by its *post-hoc* design, an imbalance in premorbid renal function between groups, and inconsistency with regards to the timing of biomarker measurement. In a non-randomized observation study of patients with severe sepsis or septic shock at a single center, those who received the combination of thiamine, vitamin C, and hydrocortisone were less likely to require RRT as compared to historical controls at the same site (3/31 [10%] vs. 11/30 [33%], $p=0.02$).²⁶ This study likewise provides some support for thiamine as a renal protective agent in sepsis, but is limited by its quasi-experimental design and the associated potential for bias.

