6.2.4 Receipt of Renal Replacement Therapy

Fisher’s exact tests will be used to compare the incidence of renal failure requiring renal replacement therapy during the index ICU stay. This outcome will be truncated at 60 days if the patient remains alive and in the ICU at that time.

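### Raw ICU stay gives early ICU deaths a favourable rank, so a mortality difference can push this key secondary outcome the wrong way

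*Protocol*

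**What the plan says.** Length of ICU stay is a key secondary outcome in the Trial Overview and in section 5.1.2. Section 6.2.6 gives its whole analysis in two sentences: "Length of ICU stay will be compared between groups using Wilcoxon Rank Sum tests", then "As in the above analyses, this will be truncated at 60 days". There is no rule for a patient who dies in the ICU.

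For RRT, section 6.2.4 uses Fisher's test to "compare the incidence of renal failure requiring renal replacement therapy during the index ICU stay". Its one special rule is "This outcome will be truncated at 60 days if the patient remains alive and in the ICU at that time". A patient who dies without RRT therefore counts as having no event.

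Four other places bear on the point:
- Sections 6.2.2 and 6.2.3 do give a rule for death, for creatinine and lactate.
- Section 6.2.5 analyses in-hospital mortality separately, by Kaplan-Meier, log-rank and Cox methods.
- The section on other biomarkers of renal injury (the second one numbered 6.2.7) names a comparison of days alive without renal failure. This outcome is not listed in section 5.1.2 or the Trial Overview.
- Section 1.1 cites, as background: "Mortality for those in septic shock with elevated lactate is more than 40" per cent. Section 1.3 adds that in one septic shock study "there was a step-wise increase in mortality with worsening AKI".

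**The concern.** On a raw-stay scale, a patient who dies on ICU day 2 ranks better than one who leaves the ICU alive on day 7. The 60-day truncation deals with very long stays, not with deaths. In a population where death is common, a treatment that prevents early deaths keeps those patients in the ICU for longer and so tends to look worse on stay. A treatment that causes early deaths tends to look better.

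In a superiority trial, a shorter stay listed as a key secondary outcome will be read as benefit. The risk is a secondary result that contradicts the mortality result, or hides a real gain, only because of how deaths are ranked.

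**Working it through.** The protocol states no rate, effect or power for ICU stay or RRT, so there is no figure to reproduce. Direction follows from reasoning; size needs assumptions.

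**Direction.** A patient whose ICU death on day t is prevented is still in the ICU on day t, so that stay can only be longer. A patient whose RRT-free death is prevented can only gain opportunity to receive RRT.

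**Inputs for ICU stay.** From the protocol: 44 per arm, two-sided 5% level, Wilcoxon test. Assumed: ICU mortality of 40% on placebo (pP) and 25% on thiamine (pT); log-normal stay with log-SD 0.8; the medians below; no treatment effect on stay within deaths or within survivors. The 60-day cap has little effect here and is left out of the formulas.

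**Formulas.**
- Let θ be the probability that a survivor's stay exceeds that of a patient who dies: θ = Φ(ln(median in survivors / median in deaths) / (0.8 × √2)).
- Probability that a thiamine stay exceeds a placebo stay: P = 0.5 + (pP − pT) × (θ − 0.5).
- Approximate standard error of the estimate of P: √(89 / (12 × 44 × 44)) = 0.0619.
- Chance that the test points to longer stay on thiamine: Φ((P − 0.5) / 0.0619).
- Chance that it is significantly longer: Φ((P − 0.5) / 0.0619 − 1.96).

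For medians of 2 and 8 days: θ = Φ(1.386 / 1.131) = 0.890; P = 0.5 + 0.15 × 0.390 = 0.558; 0.0585 / 0.0619 = 0.945; Φ(0.945) = 83%; Φ(−1.015) = 15%.

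| Median stay, deaths / survivors (days) | Mortality, placebo / thiamine | θ | P | Points to longer | Significantly longer |
|---|---|---|---|---|---|
| 2 / 8 | 40% / 25% | 0.890 | 0.558 | 83% | 15% |
| 3 / 7 | 40% / 25% | 0.773 | 0.541 | 75% | 10% |
| 5 / 7 | 40% / 25% | 0.617 | 0.518 | 61% | 4.7% |
| 3 / 7 | 40% / 35% | 0.773 | 0.514 | 59% | 4.1% |
| 7 / 7 | 40% / 25% | 0.500 | 0.500 | 50% | 2.5% |
| any | 40% / 40% | – | 0.500 | 50% | 2.5% |

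Simulation with the 60-day cap agrees to within about a percentage point (for example 60% to 61% and 4.4% to 4.6% for 5 / 7 days). If thiamine raised mortality from 40% to 55%, the first three rows hold with the sign reversed, towards shorter stay.

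**A second model.** Death and discharge were also simulated as competing events, with an unchanged discharge distribution (median 5 or 8 days, log-SD 0.8). Lowering ICU mortality from 40% to 30% moved median stay from 3.4 to 3.9 days, or from 5.5 to 6.1. The result was significantly against thiamine in 9% to 10% of trials. Lowering mortality to 20% gave about 24%. At equal mortality the test held its 5% level.

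**RRT.** In the same competing-events model the RRT hazard was equal in both arms. The placebo incidence was set at 33% (the historical-control rate in section 1.5) or, by assumption, at 20%.

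| ICU mortality on thiamine (placebo 40%) | Incidence if placebo is 33% | Incidence if placebo is 20% |
|---|---|---|
| 30% | 36% | 22% |
| 20% | 39% | 24% |
| 10% | 41% | 26% |

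The shift is about 2 to 8 percentage points. At 33% to 36% it is 0.03 × 44, or about one patient per arm.

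**The case against.** Several counter-arguments have force.

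- **The protocol is silent; it does not misstate.** It never says that deaths count as short stays, and a separate analysis plan might add a rule. But section 6.2 is headed as the statistical analysis plan, fixes the test and the truncation, and gives a death rule for creatinine and lactate. Followed as written, it produces the favourable rank.
- **Raw stay is a legitimate measure of resource use, and mortality is reported separately.** Both are true, and raw stay should remain as a description. Reporting mortality alongside helps the reader but does not correct the stay comparison.
- **The size depends on chosen assumptions.** This stands. With deaths at a median of 5 days the distortion is small. In the first model it vanishes when deaths and survivors have equal stays, and it reverses when deaths stay longer.
- **Ranking death worst partly re-tests mortality.** This also stands. Under 40% against 25% mortality, that ranking points in favour of thiamine in about 89% of simulated trials, but it does so even when deaths and survivors have identical stays. A reader might take the 89% as proof that stay is measured better; it mostly reflects the mortality difference itself.

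A reader might also infer that the protocol expects mortality above 40% in this trial. Section 1.1 is literature background, not a planning assumption, and does not say ICU mortality. Section 3.3 also excludes patients on comfort measures only or expected to have support withdrawn within 24 hours, which removes some of the earliest deaths.

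**Conclusion.** The point holds for ICU stay, conditionally. If mortality differs between arms and deaths occur earlier than discharges, the comparison in section 6.2.6 is pushed in the wrong direction. Under an assumed 40% against 25% mortality with 44 per arm, the test points to longer stay on thiamine in about 61% to 83% of trials (50% without distortion). It is significantly longer in about 4% to 15% (nominal 2.5%). With equal mortality and equal death timing there is no distortion. The mortality rates and stay times are assumptions.

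It is tempting to put RRT on the same footing. The documents do not support that: the shift is about 2 to 8 points under assumed rates, would be diluted if many patients who die receive RRT first, and is partly covered by the days-alive-without-renal-failure measure that the protocol already names. The gap there is that this measure is missing from the outcome lists.

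The primary creatinine analysis is not affected. The change is worth making because ICU stay is a key secondary outcome and the correction is cheap.

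**What to change.** **Section 6.2.6.** Make the between-arm comparison one of the following, chosen before unblinding:
- ICU-free days to day 60, with zero for patients who die in that window; or
- ICU stay with every death in the window given a rank worse than a 60-day stay.

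Keep the Wilcoxon test. Report mortality and raw ICU stay, separately for survivors and non-survivors, as descriptive components.

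State which deaths count. Section 7.1 collects most data only until death or hospital discharge, so in-hospital death up to day 60 fits the data already planned; counting later deaths would need extra follow-up.

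**Section 6.2.4.** Keep the RRT incidence comparison. Beside it, list a death-inclusive renal measure among the secondary outcomes in section 5.1.2: either days alive without renal failure, with a stated window, or RRT-or-death over the same 60-day window.

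**Cost.** Revised wording and one or two derived variables. There is no change to enrolment, treatment or sample size. The downside is that the composite mixes mortality with stay and partly repeats the mortality test, so it must always be shown with its components.

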6.2.7 Cellular Oxygen Consumption

Basal and maximum cellular oxygen consumption by peripheral blood mononuclear cells will be compared using a t-test

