4.5 Specimen collection procedures

4.5.1 Timing and volume of blood draw

All participants will have a blood samples collected at four time-points. Blood will be obtained by venipuncture, or from an existing venous or arterial catheter.

Specimen Collection Time Points

1. T1=0 hrs (just before study drug administration)
2. T2=24 hrs (+/- 4 hrs)
3. T3=48 hrs (+/- 4 hrs)

4. T4=72hrs (+/- 4hrs)

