4.5.2 Specimen samples

At the T1, T2, T3, and T4 time points, blood will be sent for complete serum creatinine and a venous/arterial blood gas to measure lactate. These tests will be performed by the clinical laboratory at each site. As many of these laboratory tests are commonly obtained for clinical purposes, these tests do not need to be repeated if a result is available from the clinical care of the participant within 4 hours of the time point.

In addition to traditional clinical markers, 20ml of blood will be obtained for future biomarker analysis (including inflammatory biomarkers, markers of endothelial function, and markers of mitochondrial function), and thiamine levels.

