5.1.2 Key Secondary Outcomes

- Incidence of Acute Renal Failure
- Length of ICU stay
- In-hospital Mortality
- Other biomarkers of renal injury (Serum cystatin C, NGAL, and KIM-1)
- Peripheral blood mononuclear cell mitochondrial oxygen consumption

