6.2.7 Other biomarkers of renal injury

Other renal injury biomarkers (cystatin C, NGAL, and KIM-1) will be measured at enrollment and 24-hours and compared using repeated measures analysis to account for within subject correlation. Days alive and free of renal failure, frequency and duration of renal replacement therapy, and hospital mortality will be compared using t-tests and chi-square tests where appropriate. Basal and maximum cellular oxygen consumption will be compared using a t-test. Analyses will be conducted on a modified intention-to-treat basis, including only those subjects who receive a dose of study drug.

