6.2.8 Subanalyses

A pre-planned subanalysis of the primary outcome will be performed in the group with baseline thiamine deficiency. Thiamine deficiency will be defined as a plasma vitamin B1 level ≤ 7 nmol/L as has been previously described.⁴⁸ The trial is not powered to detect subgroup differences, hence this analysis will be considered exploratory and hypothesis-generating.

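### PBMC oxygen consumption is assigned a plain t-test with no time point, baseline or site term, although a pre-dose research sample appears to be available

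*Protocol*

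**What the plan says.** Section 5.1.2 of the protocol includes "Peripheral blood mononuclear cell mitochondrial oxygen consumption" among the key secondary outcomes. The analysis appears twice. The section headed Cellular Oxygen Consumption says "Basal and maximum cellular oxygen consumption by peripheral blood mononuclear cells will be compared using a t-test". The next section, also numbered 6.2.7 and headed Other biomarkers of renal injury, says "Basal and maximum cellular oxygen consumption will be compared using a t-test". Neither gives a measurement time, says whether a level or a change is compared, or names a covariate.

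Section 4.5.1 schedules four blood draws, the first being "T1=0 hrs (just before study drug administration"), followed by 24, 48 and 72 hours. Section 4.5.2 assigns creatinine and lactate to all four. A separate paragraph then adds that "20ml of blood will be obtained for future biomarker analysis (including inflammatory biomarkers, markers of endothelial function, and markers of mitochondrial function), and thiamine levels". That sentence gives no time points and does not mention PBMC respiration.

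For cystatin C, NGAL and KIM-1, the second 6.2.7 section does give times and a model: they are "measured at enrollment and 24-hours and compared using repeated measures analysis to account for within subject correlation".

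**The concern.** The protocol does not leave the analysis of this outcome open. It names a test, twice, so the choice can be assessed as it stands. In a trial sized for 40 evaluable patients per arm on a different outcome (creatinine, section 6.1), a pre-dose measurement of the same quantity is usually the cheapest source of precision. The protocol uses the enrolment value for the other renal biomarkers in the same section, and repeated measures for creatinine and lactate in 6.2.2 and 6.2.3. It gives no reason for treating oxygen consumption differently.

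Site is a second, smaller point. Randomisation is stratified by site (2.2) and the creatinine model includes it (6.2.2), but a two-sample t-test does not.

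At stake are the width of the confidence interval for one secondary outcome and a choice left open: up to three post-dose draws, and level or change, all fit the stated wording.

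**Working it through.** **Is there a T1 value to adjust for?**
- Section 4.5.1 schedules a pre-dose draw.
- Section 4.5.2 introduces the 20 ml research sample as an addition to the T1 to T4 clinical tests. The sample covers markers of mitochondrial function and also supplies the thiamine level.
- Section 6.2.8 needs that thiamine level before treatment: "A pre-planned subanalysis of the primary outcome will be performed in the group with baseline thiamine deficiency".

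A pre-dose research sample is therefore the natural reading. Whether PBMC oxygen consumption is assayed on it is stated nowhere, so the rest of the check is conditional on that.

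**Inputs.** 40 evaluable patients per arm (6.1); two-sided alpha 0.05 (6.2.1). The protocol gives no effect size, SD, power or baseline-to-follow-up correlation r for this outcome. There is no stated figure to reproduce, and r is assumed over a range.

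**Formulas.** Take the variance of a t-test on the post-dose level as 1. Then:
- ANCOVA on the T1 value: 1 − r².
- t-test on change from T1: 2(1 − r).

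These ignore the small cost of estimating the slope and site coefficients.

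**Reference difference.** With 40 per arm, the post-dose t-test has 80% power for a standardised difference of (1.9600 + 0.8416) × √(2/40) = 2.8016 × 0.2236 = 0.626. For that same difference, power under variance factor f is Φ(2.8016/√f − 1.960).

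| Assumed r | ANCOVA factor | Variance removed | Equivalent sample size | ANCOVA power | Change factor | Change-score power |
|---|---|---|---|---|---|---|
| 0 | 1.00 | 0% | 1.00 | 0.80 | 2.0 | 0.508 |
| 0.3 | 0.91 | 9% | 1/0.91 = 1.10 | 0.836 | 1.4 | 0.658 |
| 0.5 | 0.75 | 25% | 1/0.75 = 1.33 | 0.899 | 1.0 | 0.80 |
| 0.7 | 0.51 | 49% | 1/0.51 = 1.96 | 0.975 | 0.6 | 0.951 |

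Example at r = 0.5: 2.8016/√0.75 = 3.235; 3.235 − 1.960 = 1.275; Φ(1.275) = 0.899.

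Two things follow. For any r above zero, ANCOVA is more precise than the post-dose t-test. And level versus change is not a neutral detail: at r = 0.3 the change-score test has power 0.658 against 0.80 for the level, while at r = 0.7 the order is reversed.

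**The case against.** The strongest reply is that the protocol never says this assay is run before treatment. Section 7.1 ties 0, 24, 48 and 72 hours to creatinine and lactate only, and section 4.5.2 describes the 20 ml as being for future work. If the assay is run once, after dosing, a two-sample t-test is an ordinary choice and no baseline value is being discarded. This stands, and it is why the recommendation is conditional.

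It can also be said that a t-test on change from T1 would use the baseline and is not excluded, and that covariates are often left to the SAP. The first is true, but it shows that the wording does not identify a single analysis. The second carries less weight where the protocol itself commits to a named test.

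The site argument is limited. Among the comparable models only creatinine names site; the lactate model and the renal biomarker analysis do not. Adding site follows from the stratification, not from a uniform practice elsewhere in the protocol.

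Finally, the outcome is key secondary only in 5.1.2. The synopsis and section 2.1 do not list it. That keeps the point minor.

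**Conclusion.** The point holds as a modest improvement in method. The stated analysis is a plain t-test with no time point, baseline term or site term, and a better one is available at almost no cost if the T1 sample is assayed. The gain is r² of the variance: 9% at r = 0.3, 25% at 0.5, 49% at 0.7, and nothing at 0. Every value of r is an assumption.

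A reader might infer more than the documents support:
- **That the planned test is biased or invalid.** It is not. Under randomisation the t-test is unbiased, and its type I error already allows for chance imbalance at baseline.
- **That a measured pre-dose value is being thrown away.** A T1 research sample is a reasonable inference; a T1 respiration assay is not stated.
- **That the trial is likely to miss a real effect, or that this outcome varies widely between patients.** The protocol gives no effect size, SD or power for it, so neither can be judged.
- **That this is the decisive mechanistic test.** Section 1.4 gives a mitochondrial rationale, but the protocol does not give the outcome that role, and its primary outcome is creatinine.

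The primary analysis is unaffected.

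**What to change.** In both sections numbered 6.2.7, state when PBMC oxygen consumption is measured and which post-dose time point is tested. Where the T1 value is assayed, replace the t-test with ANCOVA of the post-dose basal and maximum values on the corresponding T1 value and site. The repeated-measures model used for the other biomarkers, with site added, is an alternative. It gives the gain only if the post-dose contrast draws on the T1 value, for example through a T1 mean common to both arms. With complete data and a separate T1 mean for each arm, the post-dose contrast would simply return the unadjusted difference.

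The cost is about a sentence in each section and a rule for patients with no T1 assay. No extra sampling is needed if T1 is already assayed. If the assay is run only after dosing, the baseline adjustment does not apply; name the time point and add only the site term.

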6.2.7 Other biomarkers of renal injury

Other renal injury biomarkers (cystatin C, NGAL, and KIM-1) will be measured at enrollment and 24-hours and compared using repeated measures analysis to account for within subject correlation. Days alive and free of renal failure, frequency and duration of renal replacement therapy, and hospital mortality will be compared using t-tests and chi-square tests where appropriate. Basal and maximum cellular oxygen consumption will be compared using a t-test. Analyses will be conducted on a modified intention-to-treat basis, including only those subjects who receive a dose of study drug.

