2.2 Allocation

Participants will be randomized in a 1:1 ratio to either thiamine or placebo in blocks with random sizes of 2 or 4. The randomization will be stratified according to site.³⁸ An independent statistician will create the randomization list using a random number generator. The complete list will only be shared with an independent pharmacy consultant, who will not be involved in clinical care. The pharmacy consultant and the independent statistician will both store the randomization list.

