6.2 Statistical analysis plan

6.2.1 General considerations

The statistical analyses and reporting will adhere to the CONSORT guidelines.^{42,43} All tests will be two-sided, a p-value < 0.05 will be considered significant, and all confidence intervals will have 95% coverage. All analyses will be conducted on a modified intention-to-treat basis only including participants receiving at least the first dose of the study medications. In a double-blind trial, this approach is unbiased while increasing precision.⁴⁴ The two groups will be compared in relation to baseline characteristics using descriptive statistics.

The persons conducting the statistical analysis will be blinded to the randomized allocation. Groups will be designated as “A” and “B” until all pre-specified analyses are performed and shared with all authors and the Data Safety Monitoring Board.

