6.2.2 Creatinine at 72-hours

Assuming no unbalanced potentially confounding variables (as would be expected in this randomized trial), we will compare repeated measures of creatinine levels at each time point (0h, 24h, 48h, 72h) between arms using repeated measures analysis. A compound symmetry covariance structure will be used. If a patient receives renal replacement therapy or dies before any time point, creatinine levels will be imputed by carrying forward the last known value before the event. Study site will be controlled for as a fixed-effect in the regression model.

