6.2.3 Lactate at 72-hours

Assuming no unbalanced potentially confounding variables (as would be expected in this randomized trial), we will compare repeated measures of lactate levels at each time point (0h, 24h, 48h, 72h) between arms using repeated measures analysis. A compound symmetry covariance structure will be used. If a patient receives renal replacement therapy or dies before any time point, lactate levels will be imputed by carrying forward the last known value before the event.

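### Section 6.2.7 names neither the arm contrast nor the role of the enrollment value for cystatin C, NGAL and KIM-1; unless baseline means are constrained equal, precision is lost

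*Protocol*

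**What the plan says.** Protocol 5.1.2 lists among the key secondary outcomes "Other biomarkers of renal injury (Serum cystatin C, NGAL, and KIM-1". The section on other biomarkers of renal injury (the second of two sections numbered 6.2.7) gives their analysis: they "will be measured at enrollment and 24-hours and compared using repeated measures analysis to account for within subject correlation". It names no between-arm contrast, baseline covariate, condition on the enrollment means or site term.

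The first study sample is taken before treatment: section 4.5.1 defines "T1=0 hrs (just before study drug administration".

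Two neighbouring sections describe analyses of the same kind. For creatinine, 6.2.2 says "we will compare repeated measures of creatinine levels at each time point (0h, 24h, 48h, 72h) between arms using repeated measures analysis" and adds "Study site will be controlled for as a fixed-effect in the regression model". For lactate, 6.2.3 says "we will compare repeated measures of lactate levels at each time point (0h, 24h, 48h, 72h) between arms using repeated measures analysis", with no site term. Section 2.2 says "The randomization will be stratified according to site".

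**The concern.** Each marker has two values per patient. The enrollment value precedes study drug and cannot carry a treatment effect, so all the information about treatment lies at 24 h. What the enrollment value can do is explain part of the between-patient variation at 24 h and so sharpen the comparison. It does this if it is a covariate, or if the model holds the arm means equal at enrollment. It does not if both values are free responses with a separate mean per arm and time.

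Section 6.2.7 does not say which is meant. Sections 6.2.2 and 6.2.3 compare arms at 0 h as well as later, and a model that does so does not constrain the means there. That makes the unconstrained form the likelier reading for the biomarkers.

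At stake is the chance of detecting a real effect on three key secondary outcomes in a trial of 88 patients, using a baseline value that will be collected anyway. Because no contrast is named, analyses with quite different power all fit the text.

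**Working it through.** **Figure to reproduce.** There is none: the protocol states no power, effect size, SD or correlation for these markers. Its sample size (6.1) concerns creatinine at 72 h.

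**Inputs from the protocol.** 44 per arm (6.1); 1:1 allocation (2.2); "All tests will be two-sided, a p-value < 0.05 will be considered significant" (6.2.1). The enrollment value is taken to be the pre-dose T1 sample of 4.5.1.

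**Assumptions.** Equal variances at the two times; a true 24 h difference d = 0.5 SD; 44 complete patients per arm; enrollment-to-24 h correlation rho from 0.3 to 0.87. The upper value is borrowed from the creatinine variance components in 6.1, 1.3/(1.3 + 0.19) = 0.87. It is the only correlation the document implies, and it belongs to a different analyte.

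**Formulas.** Variance of the arm contrast, in units of 2σ²/n:
- 24 h level, enrollment unused: 1
- change, which with two times equals the arm-by-time contrast: 2(1 − rho)
- 24 h adjusted for enrollment: 1 − rho²

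Since 1 − rho² < 1 for rho > 0, and 2(1 − rho) − (1 − rho²) = (1 − rho)² > 0 for rho < 1, the adjusted contrast is the most precise of the three for every rho strictly between 0 and 1.

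**Power.** Two-sided noncentral t with noncentrality 0.5/√(v × 2/44), where v is the relative variance. For the level contrast this is 0.5/√(2/44) = 2.345, giving 0.640. For the adjusted contrast at rho 0.5 it is 2.345/√0.75 = 2.708, giving 0.763.

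| rho | v: level / change / adjusted | power: level / change / adjusted | gain over level | gain over change |
|---|---|---|---|---|
| 0.3 | 1 / 1.40 / 0.91 | 0.640 / 0.500 / 0.681 | 4 points | 18 points |
| 0.5 | 1 / 1.00 / 0.75 | 0.640 / 0.640 / 0.763 | 12 points | 12 points |
| 0.7 | 1 / 0.60 / 0.51 | 0.640 / 0.849 / 0.901 | 26 points | 5 points |
| 0.87 | 1 / 0.26 / 0.243 | 0.640 / 0.995 / 0.997 | 36 points | 0.2 points |

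In sample-size terms, the level contrast needs 1/(1 − rho²) times as many patients as the adjusted one: 1.10, 1.33, 1.96 and 4.11 down the table. The change contrast needs 2/(1 + rho) times as many: 1.54, 1.33, 1.18 and 1.07.

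**Fewer completers.** With 40 per arm, the number before the drop-out allowance in 6.1, rho 0.5 gives 0.598 / 0.598 / 0.722, again a gain of 12 points.

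**Arm main effect.** Averaging the two times estimates d/2 with relative variance (1 + rho)/2. Power is 0.30, 0.27, 0.24 and 0.22 at the four values of rho. The cause is the halved target. At rho 0.3 its variance is 0.65 against 0.91 for the adjusted contrast, and at rho 0.5 both are 0.75.

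**Constrained model.** A simulation with 44 per arm and 4,000 runs, with the effect set so that ANCOVA has about 80% power, gave ANCOVA against equal-enrollment-means power of 0.787 v 0.793 (rho 0.3), 0.784 v 0.790 (0.5), 0.777 v 0.782 (0.7) and 0.784 v 0.789 (0.872). The constrained model loses nothing.

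**The case against.** **The text is silent rather than wrong.** A repeated-measures model with equal arm means at enrollment also fits 6.2.7 and loses nothing, and a separate analysis plan may settle the matter. This stands in part: a reader might infer that putting enrollment among the responses necessarily costs power, and the document does not support that. However, section 6.2 presents itself as the statistical analysis plan and commits to a method for each outcome, and 6.2.2 and 6.2.3 point towards the unconstrained form. The loss is therefore conditional, and asking for the model to be stated is fair.

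**Validity is intact.** A reader might infer that a chance enrollment imbalance biases the result. Under randomization it does not: the level and change contrasts are unbiased and keep their type I error, and chance imbalance adds variance that the standard error already reflects. This stands in full.

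**The size depends on assumptions.** Every rho and the 0.5 SD effect are assumed. The large gains need the level contrast, which 6.2.7 does not name. Against a change contrast at high rho the gain is almost nil. Nor does any section propose the arm main effect, so its low power should not be read as the plan's power. All of this stands, which is why the result is given as a range.

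**Importance is limited.** The markers are in 5.1.2 but not in the synopsis list or the 2.1 overview, and the trial is powered on creatinine alone. Lactate is not a listed key secondary outcome, and no size can be given for omitting site. These points lower the priority; they do not remove the gain.

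**Conclusion.** The point holds as a conditional efficiency issue. If the enrollment means are left free, the 24 h level and change contrasts are both less precise than a baseline-adjusted 24 h comparison for any rho between 0 and 1 under equal variances. At 44 per arm and an assumed 0.5 SD effect, adjustment gains 12 points of power over either contrast at rho 0.5. Across rho 0.3 to 0.87 the gain is 4 to 36 points over level and 18 down to 0.2 points over change. If the enrollment means are constrained equal, the loss is zero.

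It does not follow that the plan is biased, that its error rate is inflated, or that every possible contrast is less precise. The case for acting is that a better-defined analysis costs almost nothing.

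**What to change.** In the biomarker section 6.2.7, name the 24 h arm difference as the reported result for each marker. Obtain it either from an ANCOVA with that marker's enrollment value and study site as covariates, or from a repeated-measures model with arm means constrained equal at enrollment, plus site. The constrained form keeps patients who lack an enrollment value; ANCOVA on observed values drops them.

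As a lower priority, make the same change in 6.2.3: report the 72 h lactate arm difference adjusted for the 0 h value (or with equal 0 h means) and site.

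The cost is a sentence in each section, with no new data and no change to sample size or procedures. The wording should be fixed before unblinding.
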